4.3 Key design features to minimise bias

(a) Confounding/allocation bias (systematic differences between baseline characteristics of the groups that are compared)

Participants will act as their own controls providing that they complete both phases of the trial, precluding confounding. The allocation sequence (order of drug and placebo in the two phases) will be randomised and concealed making prediction of the next treatment allocation difficult, minimising confounding for any order effect; this will also minimise confounding of the treatment effect for phase 1 if phase 2 proves not to be feasible. However, the small numbers of participants available for this study may introduce imbalances between the groups by chance (see section 5.1).

(b) **Performance bias** (systematic differences between groups in the care that is provided, or in exposure to factors other than the interventions of interest)

This bias will be minimised by:

- Blinding of all participants and personnel (apart from the dispensing pharmacist) and the success of blinding will be assessed (participants may become un-blinded due to side effects or marked symptomatic improvement);
- Administering the intervention, comparator and other procedures undertaken during the trial according to standard protocols;
- Pre-defining all procedures for participant follow-up and applying the procedures to all participants in the same way;
- Monitoring adherence to the protocol.
- (c) Detection bias (systematic differences between groups in how outcomes are determined)

This bias will be minimised by:

- Blinding of all individuals assessing outcomes, including cardiologists/technicians conducting the bicycle ergometry tests (i.e. peak VO₂), and participants and assessing the success of blinding;

- Using an objective primary outcome measure of peak whole body oxygen consumption on bicycle ergometry which is a well validated indicator of skeletal muscle mitochondrial dysfunction in Barth syndrome.
- (d) Attrition bias (systematic differences between groups in withdrawals from a study)

This bias will be minimised by:

- Maintaining contact with participating families throughout the duration of the trial to maximise the proportion of participants for whom all outcome data are available (see section 5.12), even if the drug or placebo intervention has to be stopped for a participant (this may be facilitated through the follow-up of patients through the Barth Syndrome Service if necessary), and the proportion of participants who receive the intervention to which they were allocated.
- Implementing measures to promote adherence to random allocations.
- Pre-specifying analysis of phase 1 only if a proportion of participants (to be specified) fail to complete phase 2.
- Using intention to treat analysis.

(e) Reporting bias

This type of bias will be minimised by having pre-specified outcomes (see section 4.6) and a pre-specified analysis plan (see section 6.0).

4.4 Trial population

The reference population is males with a confirmed diagnosis of Barth syndrome.

The study population is males aged \geq 6 years in the UK, with a confirmed diagnosis of Barth syndrome with the following inclusion/exclusion criteria applied. Males under 6 years of age are not included in this patient population because of difficulties in obtaining data on the primary outcome through bicycle ergometry in young children.

4.4.1 Inclusion criteria

Participant may enter study if ALL of the following apply:

- 1. Male aged ≥ 6 years old
- 2. Clinical diagnosis of Barth syndrome with characteristic abnormality of the L4cardiolipin/monolysocardiolipin ratio plus identified mutation in the tafazzin gene
- 3. Under the care of the NHS Barth Syndrome Service (BSS)
- 4. Stable cardiac condition
- 5. Able to swallow bezafibrate tablets (similar size to ibuprofen tablets)

4.4.2 Exclusion criteria

Participant may not enter study if ANY of the following apply:

- 1. Known hypersensitivity to bezafibrate, to any component of the product or to other fibrates
- 2. Known photoallergic or phototoxic reactions to fibrates.
- 3. Hepatic dysfunction and/or liver function tests greater than 2x normal

- 4. A shortening fraction of <25 (or a significant drop in shortening fraction in the previous year)
- 5. Documented atrial or ventricular arrhythmia (atrial/ventricular tachycardia or atrial/ventricular fibrillation) that has not been stabilised with treatment.
- 6. Renal impairment (creatinine clearance < 90 mL/min)
- 7. Pre-existing known gallbladder disease.
- 8. Recent unspecified significant deterioration in general health
- 9. Prisoners and adults lacking capacity to provide informed consent

There are reports of rhabdomyolysis occurring in patients treated with a combination of bezafibrate and statins. Four of the five males in this patient cohort who have undergone cardiac transplantation are maintained on the statin pravastatin. This has been discussed with the cardiology team at Great Ormond Street Hospital who are agreeable for this medication to be ceased during the trial period.

4.5 Trial interventions

Bezafibrate is classed as an Investigational Medicinal Product (IMP) and is therefore under the regulation of the Medicines and Healthcare products Regulatory Agency (MHRA).

All participants will receive 4 calendar months of the intervention (bezafibrate) **and** 4 calendar months of the placebo (if the trial proceeds to phase 2. See section 4.2 for details). The order in which they will be administered will depend on the allocated treatment arm at first randomisation. Those first allocated to the intervention at randomisation will be given bezafibrate followed by the placebo. Those first allocated to the placebo at randomisation will be given the placebo followed by bezafibrate. Both arms will have a minimum of 1 calendar month washout period between the intervention and placebo administered, where no treatment is given.

Participants will be dispensed at least a month's supply of either bezafibrate or placebo at any one time. For participants who live some distance away from Bristol, they will receive further dispensed medications via courier.

The study intervention will be prescribed once at the start of the study. As investigators and participants are blinded, the prescription will not specify which medication (bezafibrate or placebo) will be taken first: this will be determined by the randomisation list held by the UH Bristol Clinical Trials Pharmacy department. All dispensing will be managed by UH Bristol Clinical Trials Pharmacy Department, including cross-over to the other study medication if the study proceeds to the second phase

Intervention: Bezafibrate taken orally in tablet formulation.

- Children aged 6-9 years: Commence on 100mg OD for the first month and if well tolerated increase to 100mg BD for the remaining 3 month treatment period
- Children aged 10-17 years: commence on 200mg OD for the first month and if well tolerated increase to 200mg BD for the remaining 3 month treatment period
- Adults (≥ 18 years): 200mg BD

Placebo: Tablet formulation with no active substance taken orally. The placebo will look, taste and smell as similar as possible to the intervention.

Bezafibrate and placebo will be stored, packaged and labelled by UH Bristol Pharmacy Department. Drug accountability will also be managed and monitored by UH Bristol Pharmacy Department. Both will be performed according to their SOPs, which are in accordance with GCP.

Compliance with study treatment will be assessed by asking participants to return any unused medications.

Concomitant medication (including contraindicated medication/treatments) [14]:

- Care is required in administering bezafibrate to patients taking coumarin-type anti-coagulants, the action of which may be potentiated. The dosage of anti-coagulant should be reduced by up to 50% and readjusted by monitoring blood coagulation.
- As bezafibrate improves glucose utilisation the action of antidiabetic medication, including insulin, may be potentiated and should be considered.
- Should combined therapy with an ion-exchange resin be considered necessary, there should be an interval of 2 hours between the intake of the resin and bezafibrate, otherwise the absorption of bezafibrate may be impaired.
- In isolated cases, a pronounced though reversible impairment of renal function (accompanied by a corresponding increase in serum creatinine level) has been reported in organ transplant patients receiving immuno-suppressant therapy and concomitant bezafibrate. Accordingly, renal function should be closely monitored in these patients and, in the event of relevant significant changes in laboratory parameters, bezafibrate, should if necessary, be discontinued. (NB creatinine will be measured at 2 weeks after commencing study medication in both phases of the study in participants who have received an organ transplant.)
- MAO-inhibitors (with hepatotoxic potential) should not be administered together with bezafibrate.
- Interaction between HMG CoA reductase inhibitors and fibrates may vary in nature and intensity depending on the combination of the administered drugs. A pharmacodynamic interaction between these two classes of drugs may, in some cases, also contribute to an increase in the risk of myopathy for specific dose recommendations of statins. Refer also to the SPC of the relevant product.

Granulocyte colony-stimulating factor (GCSF): Participants will continue to be prescribed GSCF as clinically indicated as there are currently no known drug interactions with this treatment.

Blood count deterioration: if a patient is shown to have a neutrophil count below 0.5×10^9 /L, either in their monthly monitoring counts or if a participant presents with sign and symptoms of infection and requires additional blood tests as part of their normal care, GCSF therapy will be initiated or dose/frequency of dosing reviewed and possibly increased in line with routine care of these patients. Subsequent weekly full blood counts will be requested on post G-CSF days for the next two weeks (as this is the routine way of monitoring neutrophil counts in these patients). If the patient has three consecutive blood counts of less than 0.5×10^9 /L, administration of the intervention will be terminated.

Post-trial treatment: Once the participants have completed the study treatment their medical care will revert to the standard care received from the Barth Syndrome Service. However, if bezafibrate is shown to have a beneficial effect on individual participants, provision will be made for them to continue receiving bezafibrate, on a case-by-case basis.

Current licensed indications:

- Treatment of severe hypertriglyceridaemia with or without low HDL cholesterol.
- Mixed hyperlipidaemia when a statin is contraindicated or not tolerated.

Elimination half-life of drug in the body: 1-2 hours

For further information about bezafibrate please see the Investigational Medicinal Product Dossier Bezafibrate 100mg tablets and placebo Bezafibrate 100mg tablets (Version 1.0, 14/02/2018).

4.6 **Primary and secondary outcomes**

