30% of living UK patients have undergone cardiac transplantation and several of these have died of cardiac rejection or post-transplant lymphoproliferative disease; others deteriorated too fast to undergo transplantation or died of complications of ventricular assist devices or ECMO whilst awaiting transplantation. In the past five years four babies/infants have been candidates for cardiac transplantation, requiring cumulatively approximately 20 months of intensive care bed stays. Sadly only one has undergone successful transplantation due to factors including shortage of donor hearts. Even those who have not received transplants can develop life-threatening heart rhythm disturbances.

Neutropenia is another life-threatening issue due to attendant serious bacterial infection. As a result, two thirds of UK patients require chronic subcutaneous injection therapy with granulocyte colony stimulating factor (G-CSF), a distressing and expensive medication. Furthermore, the management of neutropenia in this disease is challenging since patients have highly variable neutrophil counts, preventing administration of a consistent daily dose and requiring repeated blood counts and physician oversight. They often remain intermittently neutropaenic even when receiving G-CSF.

Lethargy and fatigue are universal, interfering with schoolwork and play and often necessitating the use of wheelchairs. Similarly patients cannot hold down strenuous or demanding jobs. Many patients have major feeding problems from the neonatal period through into adult life and require long term supplemental feeding via gastrostomies.

There can be rapid deterioration during periods of stable health and when under expert medical care. Ventricular arrhythmia (tachycardia or fibrillation) affects 10% of adolescents and can

cause sudden cardiac death at any stage of childhood, including the neonatal period [3]. These seemingly random acute crises are not predictable by genotype or recent medical history, producing a need for cardiac resuscitation training and chronic anxiety in affected families.

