4.6.2 Secondary outcomes

- 1. Monolysocardiolipin/tetralinoleoyl-cardiolipin MLCL/L4-CL ratio/cardiolipin profile in blood cells
- 2. PCr/ATP ratio in cardiac muscle on 31P Magnetic Resonance Spectroscopy
- 3. Skeletal muscle oxidative function/ on 31P Magnetic Resonance Spectroscopy
- 4. Quality of life (QoL) assessed using age-appropriate PedsQL questionnaires
- 5. Absolute neutrophil count
- 6. Amino acid expression (serum arginine and cysteine levels)
- 7. Cardiac function (LVEF and shortening fraction)
- 8. Mitochondrial size in lymphocytes
- 9. Numbers of mitochondria (per lymphocyte)
- 10. Total area of mitochondria per lymphocyte
- 11. Area of mitochondria as proportion of cytoplasm
- 12. Mitochondria function and cristae organisation in lymphocytes
- 13. Arrhythmia profile from 12 lead ECG at rest and during exercise (for potential rhythm abnormalities)

See Section 5.6 Data Collection for the timing of these assessments.

The work around the immortalised cell lines does not form part of this protocol and will be described in a separate protocol.

In addition to the data collected from the clinical trial we propose to integrate qualitative research methods in order to explore patients' and families' experiences of the different interventions. Parents of younger patients (<18 yrs) and patients (>14yrs, suitability for interviewing to be determined on advice from the Clinical Psychologist known to the patient) will be invited to take part in semi-structured one-to-one interviews in the assessment periods after the first and second interventions. The first interview will last approximately 20 minutes and explore the parents'/participant's experience of the intervention. The second interview will last

approximately 40 minutes and will explore the parents'/participant's experience of the second intervention and their perception of participating in the trial as a whole. Interviews with patients and parents will be digitally recorded with their consent and transcribed verbatim. Data from interviews will be analysed using framework analysis methodology [15] with the aid of the NVivo software package.

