5.11 Frequency and duration of follow up

Follow up for this study will continue for one month after the study treatment has ended in order to assess the safety of bezafibrate in this patient population.

Monthly blood tests will be performed throughout the study to assess full blood count including absolute neutrophil count, routine renal and liver function tests, plasma triglyceride/total cholesterol/LDL-cholesterol and creatinine kinase. The latter is included since bezafibrate can induce rhabdomyolysis, although this risk is most significant in those being additionally treated with statins [17]. An additional blood test for creatinine will be carried out at 2 weeks after the initiation of study drug in both phases in participants who had had an organ transplant. Where patients are receiving GCSF for management of severe neutropenia, these tests will follow our usual testing protocol and be performed on the day following GCSF administration. This method of assessment is used since some patients will show unpredictably exuberant responses to GCSF, which is best detected using this method in order to allow dose manipulation by monitoring of "peak" rather than "trough" counts.

These safety monitoring blood tests will be performed at a GP surgery/hospital local to the participant, or an appropriate assessment visit to Bristol.

The study research nurses will have regular contact with participants to collect adverse event data: after the first week of starting treatment and then monthly thereafter until end of follow-up. Patients will be asked to report (by telephone or via the Patients Know Best web service which the Barth Syndrome Service utilise for secure electronic communication with patients / parents / guardians) any unexpected symptoms or hospital visits/admissions to the Barth Syndrome Service clinical and nursing team, or the research team. If participants require help out of

normal service hours, they may contact the on-call haematology registrar or Consultant at Bristol Royal Hospital for Children who will be able to contact one of the clinicians allied to the Barth Syndrome Service.

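### The neutrophil comparison may understate a drug effect, because G-CSF can be adjusted to the count in either phase and its use is neither a listed outcome nor a schedule item

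*Protocol*

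**What the plan says.** - **Outcome.** Item 5 of the secondary outcomes in Protocol section 4.6.2 is "Absolute neutrophil count". None of the 13 items concerns G-CSF use, dose or need.
- **G-CSF during the trial.** Section 4.5 leaves it free in both phases: "Participants will continue to be prescribed GSCF as clinically indicated". The reason given is that no drug interaction is known.
- **Response to low counts.** Section 4.5 adds that below 0.5 x 10^9/L "GCSF therapy will be initiated or dose/frequency of dosing reviewed and possibly increased in line with routine care of these patients".
- **Response to high counts.** For patients on G-CSF, section 5.11 says of the safety blood tests that "these tests will follow our usual testing protocol and be performed on the day following GCSF administration", because "some patients will show unpredictably exuberant responses to GCSF, which is best detected using this method in order to allow dose manipulation by monitoring".
- **Background use.** Section 2 states that "two thirds of UK patients require chronic subcutaneous injection therapy with granulocyte colony stimulating factor", and that "patients have highly variable neutrophil counts, preventing administration of a consistent daily dose".
- **Schedule.** Table 1 (section 5.6) lists neutrophil counts at baseline, monthly and at the end of each phase. It has no G-CSF item.
- **Analysis.** Section 6.1 fits treatment, period, the baseline value of the outcome and a random participant effect, and uses similar methods for the secondary outcomes. It allows further analyses in a later plan and does not mention G-CSF.

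**The concern.** The outcome is compared while a co-treatment that acts on it may be started or changed because of it. If bezafibrate lowers neutrophils, more participants cross the threshold in the bezafibrate phase and some receive more G-CSF, which lifts their later counts. If bezafibrate raises neutrophils, fewer need G-CSF in that phase, while low placebo-phase counts are lifted. In both cases the two phases end closer together than the drug effect alone would put them.

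Blinding does not prevent this. It keeps G-CSF decisions even-handed for a given count, but the decisions respond to the count, and the count carries the drug effect.

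A small difference in counts could then be reported as no effect on neutrophils when part of the effect lies in G-CSF use. The protocol makes this matter both ways. Section 2 calls neutropenia life-threatening and G-CSF distressing and expensive, so a lower need for injections would itself be a benefit. As written, no listed outcome would show it.

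**Working it through.** **Step 1. Is there a stated figure to reproduce?** There is none for the neutrophil count: no SD, no expected drug effect and no G-CSF dose-response. The only power figure is for peak VO2 (section 4.7): 12 participants, two-sided alpha 0.05, 0.90 SD at 80% power. It reproduces at 80.2% (noncentral t, 10 df) if the SD is that of the within-participant difference. It serves below only as a yardstick.

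**Step 2. Can G-CSF move with the count, and in which direction?**

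| Place | What it permits | Direction |
|---|---|---|
| 4.5, low-count rule | Start, or review and possible increase, below 0.5 x 10^9/L | Up only |
| 4.5, G-CSF paragraph | Prescribing on clinical grounds, both phases | Either |
| 5.11 | Dose change after an exuberant response | Implies down |

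The explicit rule works upward only. It bears mainly on a harmful effect, and narrows a beneficial one by lifting placebo-phase counts. Dose reduction rests on section 5.11 and the general clause in 4.5.

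**Step 3. Would the plan show the shift?** The outcome list, Table 1 and the section 6.1 model contain no G-CSF quantity. As written, the shift is not compared.

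**Step 4. How large could it be? Illustration only; all inputs are assumed.**

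(a) *Attenuation and power.* Let g be the share of participants whose G-CSF responds to the count and f the share of the effect offset in them. The share of the mean effect kept is 1 - g x f. Start from a true effect of 0.90 SD of the difference, n = 12, 10 df, SD unchanged:

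| g | f | Kept = 1 - g x f | Effect (SD) | Power |
|---|---|---|---|---|
| 2/3 | 0.5 | 0.667 | 0.60 | 47% |
| 2/3 | 0.8 | 0.467 | 0.42 | 26% |
| 2/3 | 1.0 | 0.333 | 0.30 | 15% |
| 1/3 | 0.5 | 0.833 | 0.75 | 65% |
| 1/3 | 0.8 | 0.733 | 0.66 | 54% |
| 1/3 | 1.0 | 0.667 | 0.60 | 47% |

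The two thirds is the protocol's figure for UK patients, not for trial participants. No value of f is in the documents.

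(b) *Simulation of monthly adjustment.* Assumed: median count 1.0 x 10^9/L; between- and within-patient SD 0.6 on the log scale; three monthly checks per phase; every count below 0.5 raises later counts by a factor of about 1.4 or 2; in the two thirds on G-CSF, either no dose cut or a cut above 2.0 or 4.0; both phases start from the same G-CSF level.

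| True ratio | Dose cuts | Observed ratio | Log effect kept |
|---|---|---|---|
| 0.50 | none | 0.64 to 0.75 | 42% to 64% |
| 0.50 | all scenarios | 0.64 to 0.85 | 24% to 64% |
| 2.0 | none | 1.58 to 1.74 | 66% to 80% |
| 2.0 | all scenarios | 1.25 to 1.74 | 32% to 80% |

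Attenuation appears in both directions and, without dose cuts, is stronger for a harmful effect, as Step 2 suggests. It is partial throughout. Acting on every low count is firmer than the protocol's rule, which says only that the dose may be increased, so in that respect the simulation leans towards too much attenuation.

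**The case against.** - **The analysis plan and case report forms are not shown.** Handling of co-medication is often left to them, and section 6.1 leaves room for further analyses. The missing Table 1 row does not prove that G-CSF goes unrecorded. This stands as a limit. However, the outcome list and schedule are protocol content, and a later analysis can use G-CSF only if someone has recorded it.
- **Counts under routine care, G-CSF included, are a coherent treatment-policy comparison.** That is true, and it fits the stated intention-to-treat principle. It answers what happens to the count, not whether the count was reached with more or less G-CSF. The companion measure supplies the second part.
- **Safety does not rest on this outcome.** Counts are checked monthly, low counts trigger weekly repeats, and three consecutive low counts end the intervention (4.5). The monitoring committee receives adverse event reports (6.3, 8.1). This largely stands: severe harm would probably surface. A moderate shift absorbed by extra G-CSF might not.

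Three stronger readings are tempting and are not supported:

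1. *That the count is fully controlled, so the comparison is empty.* The rule sets no target, acts only below one threshold, and says the dose is possibly increased. Section 2 adds that patients are often intermittently neutropenic despite G-CSF.
2. *That a definite share of the effect, such as one third to two thirds, is lost.* Any such figure multiplies the UK usage share by an assumed offset.
3. *That relying on one end-of-phase count is an error.* Sections 4.6.2 and 5.6 do not fix which of the scheduled counts enter the model.

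**Conclusion.** The concern holds in a limited form. G-CSF may respond to the neutrophil count in either phase, and the protocol lists no outcome or schedule item that captures its use. A drug effect on neutrophils may therefore be partly shifted into G-CSF use and understated in the count comparison. This rests on the text of sections 4.5, 4.6.2, 5.6, 5.11 and 6.1, and on the assumption that clinicians act on the counts as those sections allow.

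The size cannot be computed from the documents. The simulated scenarios keep 24% to 80% of a halving or doubling on the log scale; these are illustrations, not estimates. The point affects one of 13 secondary outcomes and leaves the primary outcome untouched. It is a cheap improvement, not a flaw that endangers the trial.

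**What to change.** 1. Record G-CSF dose and frequency during each treatment phase, including the dose on entry to the phase so that a start or an increase can be identified. Add the item to Table 1.
2. Add G-CSF use per phase to the secondary outcomes, compared by treatment: for example, any start or increase (yes/no) and cumulative dose. Many values will be zero in about 12 participants, so use a method that tolerates this, such as a rank-based comparison of within-participant differences, rather than the normal-theory mixed model.
3. State that this outcome and the end-of-phase count are read together. A similar count reached with more or less G-CSF is not to be reported as no effect.
4. Optionally, use the month 2-4 and 7-9 counts as repeated measures in a sensitivity analysis. This reduces noise but does not remove the masking, since those counts are open to the same adjustment. Months 1 and 6 are left out because under-18s are then on the first-month dose described in section 4.5.

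Clinical G-CSF rules are unchanged. The cost is a little data entry from treatment records and one extra secondary analysis, which will be imprecise at this sample size.
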